Their responses will result in one of three outcomes, “OK to Use,” “Do Not Use,” or “Ask a Doctor.” A “Do Not Use” outcome will result when the participant enters information into the app that indicates they met the *Pregnancy Alert, Do Not Use, or Stop Use* conditions listed in the DFL. They will also receive a “Do Not Use” outcome if their LDL-C retest shows an increase in the LDL-C or they enter two LDL-C retest results that demonstrate an inadequate response (i.e., $\geq 0\%$ and $< 15\%$ reduction). For inadequate responses, the participant is instructed through the Web App and transactional emails to retest within 3 months. Note that the Web App instructs people with an initial inadequate response to take one of the following actions:

- If the participant has been compliant with dosing, they are instructed to see a doctor.
- If the participant has NOT been compliant with dosing, they are instructed to be compliant and to retest within 3 months.

Participants who have no change or an increase in LDL-C will be immediately stopped from repurchasing drug. These individuals will not be eligible for a retest.

The ability to leverage technology to re-assess consumers at the time of each purchase is unprecedented in the current OTC environment and offers an important safety check to ensure that the key requirements for continued use are met.

Because of the importance of the first co-primary endpoint in establishing that Crestor OTC can be correctly self-selected and the second co-primary endpoint showing appropriate use

without the oversight of a healthcare provider, the threshold for success for both was set at a point estimate of 90% with a lower bound of 85%. Meeting this rigorous threshold will provide a high level of confidence that the right consumers will be able to properly self-select and use Crestor OTC when it is available without a prescription.

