9.2 Sample Size Determination

The sample size is based on powering the study for the co-primary endpoints. The evaluation of the first co-primary endpoint on the Overall Correct Initial TASS Outcome will have a sample size of approximately 1220; however, not all of these participants may have an Overall Correct Initial TASS Outcome. As part of the primary analysis of this endpoint, any participants with a missing Overall Correct Initial TASS Outcome will be imputed using worst case imputation (i.e., as incorrect). As such, it is unknown exactly how the true self-selection rate will be affected based on this imputation. Therefore, the resulting power assuming various true self-selection rates in order to demonstrate that the LB of the 95% exact binomial confidence interval (CI) is greater than 85% with a sample of approximately 1220 participants is presented in the table below:

True Self-Selection Rate	Power	True Self-Selection Rate	Power
88.24%	90%	88.57%	95%
88.30%	91%	88.67%	96%
88.35%	92%	88.78%	97%
88.42%	93%	88.93%	98%
88.49%	94%	90.00%	>99%

Evaluation of the second co-primary endpoint on the Overall Correct Final Use Outcome will have a sample size of at least 500 participants. A sample size of 500 participants would provide at least 90% power to demonstrate that the lower bound of the 95% exact binomial CI is greater than 85% for the final use endpoint, assuming that the true correct final use outcome rate is 90%. It is anticipated that at least 450 participants will be included in the evaluation of the third co-primary endpoint of PCFB in verified LDL-C to Visit 2. Assuming a true mean PCFB of -25% with a standard deviation of 25%, a sample size of 450 participants would provide greater than 99% power to demonstrate that the upper bound of the two-sided 95% confidence interval on the mean PCFB in verified LDL-C to Visit 2 is less than -15%.

It is expected that approximately 80,000 consumers will contact the Call Center for pre-screening in response to advertising. Traditional (i.e., television, print) and digital advertising approaches will be utilized for recruitment. The table below summarizes the estimates and percentage drops at each step from the initial call into the Call Center through completion of the study.

Table 3 **Estimated Number of Subjects/Participants by Study Stage**

Calls into Call Center	Estimated 80,000 calls
Sent the Web Link Assumes: Pre-screen Fail rate = 24% Qualified Refused rate = 8%	Estimated 54,400 subjects

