9.4.2 Study Endpoints

9.4.2.1 Primary Endpoint(s)

The first co-primary analysis will evaluate the percentage of participants who achieved an Overall Correct Initial TASS Outcome at the initial self-selection. The Self-Selection (SS) population will be the primary population used for this analysis; however, a second evaluation using the AUS ITT population and PP population will also be performed. The second co-primary analysis will evaluate the percentage of participants who achieved an Overall Correct Final Use Outcome at the final use assessment. The Per Protocol (PP) population will be the primary population used for this endpoint analysis (see Section 9.3 for definitions of analysis populations). For these evaluations, the outcomes obtained by the participant will be compared to the outcomes obtained by the CMOG clinician following verification of the participant's medical and laboratory data. The third co-primary analysis will evaluate percent change from baseline (PCFB) in verified LDL-C values to Visit 2 in participants in the AUS ITT population regardless of their final use outcome.

The three co-primary endpoints are evaluated as follows:

- 1 Percentage of participants with an Overall Correct (correct + mitigated) Initial TASS Outcome at the initial self-selection, defined as the number of participants with a correct *initial* TASS outcome divided by the number of participants in the analysis population (Threshold: 85% LB). Those participants with a missing CMOG clinician initial TASS outcome will be counted as Incorrect for the endpoint. This will be calculated as follows:

$$\text{Overall Correct Initial TASS Outcome (\%)} = \frac{C_S + C_{AAD} + M_{RAP} + M_{RPS}}{\# \text{ of participants in the analysis population}}$$

A 95% confidence interval will be computed using exact binomial methods (i.e., Clopper-Pearson) for the proportion of each correct outcome among the entire SS Population.

[Figure 2](#) below provides a matrix of Correct and Incorrect Selectors or Ask a Doctor based on the participant and CMOG clinician TASS outcomes for the initial TASS assessment.

Figure 2 Two-by-Four Table Illustrating Possible Self-Selection Outcomes for Initial TASS Assessment

		CMOG Clinician Verified Initial TASS Outcome			
		Ok to Use	AAD	Do Not Use	Missing
Participant Initial TASS Outcome	Ok to Use	Correct Selection (Cs + MCs)	Incorrect Selection	Incorrect Selection	Incorrect Missing

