	AAD	Incorrect AAD	Correct AAD (CAAD +MCAAD)	Incorrect AAD	Incorrect Missing

The primary analysis for the Overall Correct Initial TASS Outcome will be reported as follows:

	Analysis Population (N=XXX)		
	N	%	95% CI
Overall Correct Initial TASS Outcome	XX	XX%	(LB%, UB%)
Correct Selectors	XX	XX%	(LB%, UB%)
Correct AAD	XX	XX%	(LB%, UB%)
MR _{ap}	XX	XX%	(LB%, UB%)
MR _{ps}	XX	XX%	(LB%, UB%)

where,

- Correct Selectors (Cs) = Obtain a correct TASS outcome that they qualify for Crestor OTC by receiving an 'OK to Use' screen in the TASS (compared to the CMOG clinician evaluation)
- Correct AAD (CAAD) = Obtain a correct TASS outcome that they must ask a doctor before qualifying for Crestor OTC by receiving an 'Ask a Doctor' screen in the TASS (compared to the CMOG clinician evaluation)
- MR_{ap} = Mitigated results *a priori*
- MR_{ps} = Mitigated results post-study (should there be any post-study mitigations).

The primary analysis of the first co-primary endpoint will be based on a worst case scenario missing data imputation where all participants in the respective analysis population with a missing CMOG clinician initial TASS outcome will be counted as Incorrect for the endpoint. An additional secondary analysis of this endpoint will be conducted based on the AUS ITT population. In addition to the worst case scenario analysis for the first co-primary endpoint, sensitivity analyses will be performed on the participants in the SS population with a non-missing initial TASS outcome for the CMOG clinician (i.e., complete case analysis) and with missing Overall Correct Initial TASS Outcome data imputed using best case imputation and a tipping point analysis. Further details for those participants (or CMOG clinician) with missing initial TASS outcomes and the sensitivity analyses will be described in the study SAP.

2 Percentage of participants with an Overall Correct (correct + mitigated) Final Use Outcome at the final use assessment, defined as the number of participants with a correct *final* use outcome divided by the number of participants in the analysis population with a non-missing final use outcome for both the participant and CMOG clinician (Threshold: 85% LB). This will be calculated as follows:

$$\text{Overall Correct Final Use Outcome (\%)} = \frac{C_S + C_{AAD} + C_R + M_{RAP} + M_{RPs}}{\text{\# of participants in the analysis population with a non-missing final use outcome for both the participant and CMOG clinician}}$$

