 - MC_{AAD} = Mitigated Correct Ask A Doctor
- Mitigated results post-study (MR_{PS})
 - MC_S = Mitigated Correct Selector
 - MC_{AAD} = Mitigated Ask A Doctor

The denominator for the primary analysis of the first co-primary endpoint will include those participants in the respective analysis population (SS population for the primary analysis and the AUS ITT population for the secondary analysis of this endpoint). Those participants with a missing CMOG initial TASS outcome in the SS population will be counted as incorrect for the endpoint. The target threshold for this endpoint is that the lower bound of the 95% exact confidence interval needs to be greater than 85% overall.

For the initial selection, the point estimate (PE) of the Overall Correct Initial TASS Outcome will be reported and the two-sided 95% confidence interval will be computed using exact binomial (Clopper-Pearson) methods for the proportion of each correct outcome among the entire SS population overall and by subgroups. This analysis will be repeated on the AUS ITT population overall and by subgroups. For the *a priori* and post-study mitigations, the PE and the two-sided 95% confidence interval will be computed for each TASS outcome (Cs and C_{AAD}) that was mitigated.

The above analysis will be repeated for the Overall Correct Initial TASS Outcome without any mitigations overall and by subgroups and with *a priori* mitigations only for the SS population overall and by subgroups and the AUS ITT population overall and by subgroups.

For those participants with an initial TASS outcome of “Ok to Use” or “Ask a Doctor” the count and percentage of reasons for the participant outcomes will be summarized overall and by subgroups. For participants who, after completing the Targeted Medical and Medication History form at Virtual Visit 1, have an initial CMOG outcome of “OK to Use,” “Ask a Doctor,” or “Do Not Use,” the count and percentage of reasons for the CMOG outcomes will be summarized overall and by subgroups. This analysis will be repeated on the AUS ITT and PP populations overall and by subgroups.

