 - MC_R = Mitigated Correct Rejector

The denominator for the primary analysis of the second co-primary endpoint will only include those participants in the analysis population with a non-missing final use outcome for the participant and CMOG. The target threshold for this endpoint is that the lower bound of the 95% exact confidence interval needs to be greater than 85% overall.

For the second co-primary endpoint, the PE of the Overall Correct Final Use Outcome, with *a priori* and post-study mitigations, will be reported with a two-sided 95% confidence interval which will be computed using exact binomial (Clopper-Pearson) methods for the proportion of each correct outcome among the entire PP population, with mitigations, overall and by subgroups. The Overall Correct Final Use Outcome will also be evaluated without mitigations and with only *a priori* mitigations on the PP population overall and by subgroups.

An additional exploratory analysis of the Overall Correct Final Use Outcome, with *a priori* and post-study mitigations, will be performed on the PP population for those participants who had both a participant and CMOG final use assessment obtained solely from the Web App. The PE of the Overall Correct Final Use Outcome, with *a priori* and post-study mitigations, will be reported with a two-sided 95% confidence interval which will be computed using exact binomial (Clopper-Pearson) methods for the proportion of each correct outcome among the entire PP population overall and by subgroups. Overall Correct Final Use Outcome obtained

solely from the Web App TASS assessments will also be evaluated without mitigations and with only *a priori* mitigations on the PP population overall and by subgroups.

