Any missing Overall Correct Final Use Outcomes will be imputed using best case and worst case imputation. The PE of the Overall Correct Final Use Outcome will be reported, and the two-sided 95% confidence interval will be computed using exact binomial (Clopper-Pearson) methods for each of these imputation methods. For the *a priori* and post-study mitigations, the PE and the two-sided 95% confidence interval will be computed for each TASS outcome (C_S , C_{AAD} and C_R) that was mitigated on the AUS ITT population overall and by subgroups (Sensitivity Analysis #1).

LDL-C

Unless otherwise specified, all LDL-C analyses are performed using source document verified or study mandated LDL-C values.

The third co-primary endpoint is the percent change from baseline (PCFB) in verified LDL-C values to Visit 2 in participants regardless of their final use outcome. PCFB in verified LDL-C to Visit 2 is computed as follows:

$$\text{PCFB} = \frac{100 * (\text{Verified LDL-C value at Visit 2} - \text{Verified LDL-C value at Baseline})}{\text{Verified LDL-C value at Baseline}}$$

where the verified LDL-C value at initial selection will serve as Baseline. The LDL-C values assessed as part of a re-order assessment and verified by the CMOG at Virtual Visit 2 will be used as the Visit 2 value. If a participant has more than one LDL-C retest during the use period, the most recent verified LDL-C value will be used in the analysis. Negative values in PCFB represent a decrease in LDL-C.

The PCFB in verified LDL-C to Visit 2, along with the raw values for verified LDL-C at Baseline and Visit 2, values will be summarized using descriptive statistics and a two-sided 95% confidence interval on the AUS ITT population overall and by subgroups. The target threshold for this endpoint is that the upper bound of the 95% confidence interval on the mean PCFB in the overall analysis needs to be less than -15%, with a PE less than or equal to -20%. There will be no hypothesis testing of this endpoint in the subgroups.

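### Protocol 3.1 adds a 90% point estimate to the success threshold for the first two co-primary endpoints; every other section and the SAP require only a lower bound above 85%.

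*Protocol*

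**What the plan says.** Protocol 3.1 (Endpoint Rationale), on co-primaries 1 and 2: "the threshold for success for both was set at a point estimate of 90% with a lower bound of 85" percent. Its next sentence treats this as something to be achieved: "Meeting this rigorous threshold will provide a high level of confidence".

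Protocol 9.4.2.1 gives a different threshold for each endpoint:
- Co-primary 1: "divided by the number of participants in the analysis population (Threshold: 85% LB".
- Co-primary 2: "with a non-missing final use outcome for both the participant and CMOG clinician (Threshold: 85% LB".

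SAP 4.2.2 says of co-primary 1: "The target threshold for this endpoint is that the lower bound of the 95% exact confidence interval needs to be greater than 85% overall". It uses the same words for co-primary 2: "the lower bound of the 95% exact confidence interval needs to be greater than 85% overall". The Synopsis, Protocol Sections 3 and 9.1 and SAP 1.3 also give the lower bound alone.

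For the third co-primary (LDL-C), SAP 4.2.2 does state two conditions: the upper confidence limit "needs to be less than -15%, with a PE less than or equal to -20" percent. Protocol 9.4.2.1 does the same.

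In Protocol 9.2 the figure of 90% appears for co-primary 2 as a planning value: "assuming that the true correct final use outcome rate is 90" percent. For co-primary 1 it is the last of ten tabulated true rates.

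**The concern.** The current protocol text states the decision threshold for two of the three co-primary endpoints in two ways. Section 3.1 does not present 90% as an assumption. It makes it part of the threshold, and its next paragraph uses the same two-part form for LDL-C, where the point estimate is a real requirement. A reader could fairly take the 90% as a requirement too.

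The SAP leaves the analyst no doubt. The risk is in interpretation: an observed rate of, say, 89% on either endpoint at the planned size would succeed under the SAP and fall short of Section 3.1. If the sentence were corrected only after such a result was known, the correction could look like a relaxed criterion.

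**Working it through.** **Inputs.** Planned sizes of 1,220 (co-primary 1) and 500 (co-primary 2), the ten tabulated true rates for co-primary 1, and the assumed true rate of 90% for co-primary 2, all from Protocol 9.2. The 85% null value and the two-sided 95% Clopper-Pearson interval are from Protocol 9.1.

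**Step 1: smallest passing count under the lower-bound rule.** For x correct out of n, the lower limit is the 0.025 quantile of a Beta(x, n − x + 1) distribution. Find the smallest x for which it exceeds 0.85.

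- n = 1,220: x = 1,062 gives 85.03%; x = 1,061 gives 84.95%. Cut-off 1,062/1,220 = 87.05%.
- n = 500: x = 441 gives 85.04%; x = 440 gives 84.82%. Cut-off 441/500 = 88.2%.

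**Step 2: reproduce the stated power.** Power = P(X ≥ cut-off), with X binomial(n, true rate). For n = 1,220:

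| True rate | Stated power | Exact, lower bound only |
|---|---|---|
| 88.24% | 90% | 90.8% |
| 88.30% | 91% | 91.8% |
| 88.35% | 92% | 92.6% |
| 88.42% | 93% | 93.7% |
| 88.49% | 94% | 94.6% |
| 88.57% | 95% | 95.5% |
| 88.67% | 96% | 96.4% |
| 88.78% | 97% | 97.3% |
| 88.93% | 98% | 98.2% |
| 90.00% | >99% | >99.9% |

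For n = 500 at a true 90%, P(X ≥ 441) = 91.9%, against a stated minimum of 90%. The plan's figures are correct for the lower-bound rule.

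**Step 3: the same calculation under the Section 3.1 wording.** The section does not say \"at least\"; I read it as an observed rate of 90% or more. The counts needed are 0.90 × 1,220 = 1,098 and 0.90 × 500 = 450. Their lower limits are 88.2% and 87.0%, so the point estimate would decide the outcome and the 85% bound would have no effect.

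- n = 1,220, true 90%: P(X ≥ 1,098) = 52.4%.
- n = 1,220, true 88.24%: 2.9%, where the plan states 90%.
- n = 500, true 90%: P(X ≥ 450) = 53.8%.

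**Step 4: where the two wordings disagree.** The bands are 1,062 to 1,097 of 1,220 (87.05% to 89.92%) and 441 to 449 of 500 (88.2% to 89.8%). The chance of landing in a band is the difference between the two tail probabilities:

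| True rate | n = 1,220 | n = 500 |
|---|---|---|
| 89% | 98.5% − 14.2% = 84% | 74.3% − 26.4% = 48% |
| 90% | 99.96% − 52.4% = 48% | 91.9% − 53.8% = 38% |
| 91% | >99.9% − 89.7% = 10% | 98.6% − 80.7% = 18% |
| 92% | >99.9% − 99.5% = 0.5% | 99.9% − 95.5% = 4% |

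**Step 5: which text is out of line.** Section 9.1 names no point-estimate condition for the correct-outcome endpoints, but it names none for LDL-C either, so that silence proves nothing. Two other facts do carry weight. First, Protocol 9.4.2.1 and SAP 4.2.2 attach a point-estimate condition to LDL-C and none to the other two endpoints. Second, the stated power fails under the Section 3.1 wording, and nine of the ten tabulated rates for co-primary 1 lie below 90%. The LDL-C power does not fail in that way: with the planned SD of 25% and n = 450, the standard error is 25/√450 = 1.18 points. The −20% condition lies 5/1.18 = 4.24 standard errors from the assumed −25%, so power stays above 99% with that condition added.

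**The case against.** The strongest reply is that the operative rule is already clear. Section 3.1 is a rationale section. The endpoint tables, hypotheses, endpoint definitions and SAP criteria all agree, and Protocol 9.4 gives the SAP the more detailed account of the analysis. That stands, and it limits the point: no analysis or power figure is wrong.

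A second reply is that intent cannot be read from the documents. Only co-primary 2 has an assumed rate of 90%, yet Section 3.1 applies the figure to both endpoints. So the explanation that a planning value slipped into the threshold is an inference. That also stands. The case for the lower-bound rule does not depend on it, because it rests on the contrast with LDL-C and on the power figures.

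A third reply is that requiring an observed rate at or above the true rate gives power near 50% at almost any size, and that the disagreement figures depend strongly on the true rate. Both are true. By 92% the disagreement has nearly gone; at 89% it is larger than at 90%. The 52.4% and 53.8% show that the plan was not built on the Section 3.1 wording. They do not describe a loss of power in the trial.

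**Conclusion.** The inconsistency is real and should be fixed. Section 3.1 misstates the decision threshold for two co-primary endpoints, and the rest of the plan supports the lower-bound rule. At a true rate of 90%, about 48% of results for co-primary 1 and 38% for co-primary 2 would fall where the two wordings disagree.

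These figures rest on the planned sizes of 1,220 and 500 and on reading the 90% as an observed rate of at least 90%. The cut-offs will move with the numbers actually analysed.

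**What to change.** Before database lock, amend the sentence in Protocol 3.1 so that success on each of the two endpoints means a lower limit of the two-sided 95% exact interval above 85%, as in 9.1, 9.4.2.1 and the SAP. Mention 90% only as a planning value: the assumed true rate for co-primary 2 and one of the tabulated rates for co-primary 1.

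If the sponsor did intend an observed 90% as a requirement, it would have to be added wherever the threshold is stated and the power restated; nothing outside Section 3.1 points that way.

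The cost is one sentence, with whatever amendment approval applies under Protocol Appendix A 1. No participants, data, analyses, power figures, hypotheses or SAP text need to change.

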4 STUDY DESIGN

4.1 Overall Design

This is a 6-month, single-arm, interventional, phase III SS and AUS using a TASS tool within a Web App. It is an open-label study using non- prescription rosuvastatin 5 mg in participants who qualify for treatment based on the medical and medication history, laboratory and blood pressure (BP) data they enter into the Web App. The study will enroll approximately 1,220 participants who will ultimately receive an “OK to Use” outcome using the Web App. Of these, an estimated 1,000 participants will ultimately proceed to the use phase. Note that some individuals may initially get an “Ask a Doctor” outcome because of a potential issue with treatment identified following the TASS assessment. If they ask a doctor about the potential issue, and the doctor gives them permission to order drug, they can go back into the app and retake the TASS assessment. When they confirm the doctor has given permission, they will be able to proceed to the use phase. Subjects who have a “Do Not Use” outcome or an “Ask a Doctor” outcome and do not confirm within the Web App that they spoke to a doctor will not be permitted into the home use phase of the study. CCI

CCI

After the enrollment visit, the participant will enter a 6-month use period where they will re-purchase study drug available only through an online purchase via the Web App. Participants will be required to complete a TASS reorder assessment to confirm they are still “OK to Use” prior to re-purchase. Participants will be instructed to use an eDiary to record when they took study drug, have changes to any medications and have any changes in health status. The CMOG clinician will perform a telephone status check with participants at 60 and 120 days to assess any changes in health and/or medications as well as any additional study-related issues (no instruction will be provided regarding the use of the product). Virtual Visit 2 will be completed according to the procedures described in the Schedule of Activities (SoA), Section 1.3 and details provided in Section 8 of the protocol. A 30-day follow-up phone call will be performed after study drug completion/discontinuation to assess participants status with regard to AEs.

